597 2. Participants can be withdrawn from the trial at the discretion of the Investigator due to
 598 safety concerns of if judged to be non-compliant with the trial protocol.

599 3. Pregnancy or intention of becoming pregnant

600 4. If target treatment dose of the randomized product is not tolerated by the subject.

601 5. If the trial investigator suspects acute pancreatitis, the trial drug will be discontinued until
 602 the confirmatory tests (clinically indicated laboratory and imaging) have been conducted
 603 and appropriate treatment has been administered. We anticipate confirmation within 72
 604 hours. If acute pancreatitis is confirmed, the participant will be withdrawn from the trial.
 605 If acute pancreatitis is not confirmed, the participant will resume the trial drug at the
 606 same dose previously used before temporary discontinuation.

607 6. Temporary trial drug discontinuation criteria:
 608 - Side effects to trial medication (until such side effects have resolved or have
 609 been otherwise addressed)
 610 - Acute illness requiring treatment or hospitalization
 611 - The longest time that the subject can be off trial drug and still continue in the trial
 612 is 4 weeks. If the trial drug is discontinued for >72 hours, then the dosing
 613 escalation regimen will be restarted at 0.6 mg daily and titrated up according to
 614 prescribing information recommendations.

616 **Subject Replacement**

617 Participants will not be replaced if they withdraw or become ineligible but they will be asked to
 618 return at the end of the trial period to complete the follow-up imaging/laboratory testing and
 619 analyzed in an intention to treat analysis. As up to a 28% drop-out rate is anticipated, enrolment
 620 will account for expected drop-out to minimize loss to follow-up given that subjects will not be
 621 replaced.

623 **Rationale for Trial Population**

624 The trial population represents the target population for which liraglutide is approved for chronic
 625 weight management in adult patients, with the additional inclusion criterion of a diagnosis of
 626 metabolic syndrome. This important criterion has been selected to enrich the trial population
 627 with participants with a high visceral adipose tissue burden in order to improve the statistical
 628 power to observe a meaningful effect on visceral adipose mass and enrich the trial population
 629 with individuals at high risk for cardiovascular disease.

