631 **Imaging Assessments**

632 The primary and secondary endpoints of visceral fat, abdominal subcutaneous fat, lower body
 633 fat, liver fat, and total body fat and fat-free (lean) mass will be assessed using a Phillips 3T MRI
 634 system utilizing a two point Dixon fat-water segmentation technique (Advanced MR Analytics,
 635 Sweden).²¹ This MRI system has been extensively studied and validated in multiple cohorts,²¹⁻²³
 636 has excellent test/retest precision and reliability,²⁴ and is rapid (<6 minutes) and therefore cost
 637 effective.

638 **STATISTICAL CONSIDERATIONS:**

641 **Sample Size Calculation:**

642 This trial is powered to detect a clinically meaningful difference in the placebo-corrected relative
 643 reduction in VAT. The estimates used in the sample size calculations below are derived from

644 prior data from the SCALE program. Assuming a mean 8% relative reduction of VAT among
 645 placebo treated subjects and an expected 16% relative reduction of VAT among liraglutide
 646 treated subjects (with a standard deviation of 16%, based on data from [2]), we expect to require
 647 128 total subjects (in a 1:1 trial drug:placebo randomization scheme) to achieve 80% power to
 648 detect an 8% difference between groups at an alpha level of 0.05. Assuming an estimated 28%
 649 of subjects may withdraw trial medication during the trial, we expect a planned total of 178
 650 patients will be randomized in order to achieve at least 128 completers of the full trial protocol.
 651

Placebo-corrected Effect Size	Power		
	80%	85%	90%
Sample Size (Total N, 1:1 randomization)			
5%	322	368	432
8%	128	146	170
10%	82	92	108

652
 653 **Statistical Methods:** A formal statistical analysis plan will follow. Briefly, baseline
 654 characteristics between liraglutide and placebo treated groups will be compared using
 655 appropriate parametric or non-parametric tests depending on the distribution of the data. The
 656 primary outcome will be analyzed using an intention to treat analysis. Mean change in outcome
 657 measurements will be compared between groups using the appropriate statistical test.
 658 Outcomes will also be analyzed by subgroups including age (above/below median), sex, race
 659 (non-Hispanic black, non-Hispanic white, and Hispanic), BMI category (overweight, class I
 660 obese, class II/III obese), and prediabetes status (yes/no). In order to minimize type II error in

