 661 subgroup analyses by race, we will attempt to ensure Hispanics comprise at least 25% of the
 662 trial population. A pre-specified analysis stratified by those who did vs. did not lose $\geq 4\%$ body
 663 weight at 16 weeks of treatment will be performed prior to unblinding to determine differential
 664 outcomes among “responders” vs. “non-responders” as outlined in the package insert. All
 665 statistical tests are two-sided at a 5% significance level.
 666

667 **Interim Analysis:** No interim analysis will be performed.
 668

669 **Missing Data:** The preferred approach to missing data is to incorporate proactive standard
 670 operating procedures to mitigate the likelihood of missingness. We will implement measures to
 671 reduce missing data (both baseline and endpoint). The statistical analysis plan will describe
 672 analytical approaches to address missingness of data, including multiple imputation including
 673 the last observation carried forward (LOCF) and mixed-effects model repeated measure
 674 approaches. Sensitivity analyses will also be performed to determine the effect of missingness
 675 on the primary and secondary outcomes.
 676

DATA HANDLING AND RECORD KEEPING:

677 Subjects will be assigned an identification code. A subject's name and code will be contained
 678 within a small notebook and will be kept in a locked cabinet in the research coordinator's locked
 679 office. The research chart will contain personal health information and will be kept in locked file
 680 cabinet in the research coordinator's locked office. All other data on a computer will be de-
 681 identified with the subject's identification code. Blood samples waiting for analysis will not be
 682 labeled with the subject's name, but with the assigned identification code. The trial database will
 683 be password protected. No data will be sent over the internet unless it is encrypted. All email
 684 with subject-identifiable information will be password protected. Only key personnel will have
 685 access to the information in the trial database on an as-needed basis. Key personnel may not
 686

687 alter the data in the database or directly view all of it without specific cause and approval of the
688 PI.

689

690 **ETHICS:**

691

692 **Informed Consent**

693 Before screening takes place subjects will be provided with written and verbal information about

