 912 dose will be gradually escalated to 3.0 mg starting with 0.6 mg and with a dose level increment
 913 of 0.6 mg every 7 days.

914

915 If the subject is not eligible for randomization, the subject is considered a screening failure and
 916 the subject will be registered as a screening failure in the computerized randomization
 917 system.

918
 919 At this visit, they will undergo all baseline anthropometric, imaging, and laboratory assessments.
 920

921 **The following will be recorded in the CRF:**

- 922 • Age
- 923 • Sex
- 924 • Race/ethnicity
- 925 • Weight
- 926 • Height
- 927 • Concomitant medications
- 928 • Blood Pressure
- 929 • Pulse
- 930 • Waist Circumference
- 931 • Hip Circumference
- 932 • Visceral adipose tissue mass
- 933 • Abdominal subcutaneous adipose tissue mass
- 934 • Total fat mass
- 935 • Total fat-free mass
- 936 • Lower body adipose tissue mass
- 937 • Hepatic fat content
- 938 • Laboratory tests, including
 - 939 - Markers of insulin resistance: fasting blood glucose, insulin
 - 940 - Markers of inflammation: CRP
 - 941 - Lipids: TG/HDL-C ratio,
 - 942 - Natriuretic peptides: NT-proBNP

943
 944 **Visits 4-7**

945 At Visits 4-7, subjects will follow a dose escalation regimen and trial staff will monitor for AEs
 946 and ensure adherence to diet and exercise recommendations. Subjects will follow a fixed dose
 947 escalation. The dose will be gradually escalated to 3.0 mg starting with 0.6 mg and with a dose
 948 level increment of 0.6 mg every 7 days.

949

950 **Visits 8-15**

951 Visits 8-15 are the maintenance phase of the trial. Subjects will attend visits with trial staff every
 952 4 weeks to ensure adherence to the trial protocol, monitor for AEs, monitor for non-adherence to
 953 trial medication, and monitor adherence to diet and exercise recommendations.

954

955 **Visit 16**

956 Visit 16 is the final visit during the maintenance phase during which follow-up imaging and
 957 laboratory studies will be assessed in addition to assessments done during Visits 8-15. All
 958 remaining doses of trial medication will be collected at this visit and returned to Novo Nordisk.
 959 No further trial drug will be administered after this visit.

960

961 **The following will be recorded in the CRF:**

- 962 • Weight

- 963 • Height
- 964 • Concomitant medications
- 965 • Blood Pressure
- 966 • Pulse
- 967 • Waist Circumference
- 968 • Hip Circumference
- 969 • Visceral adipose tissue mass

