- 1350 • More frequent (>10%): nausea, diarrhea, constipation, and vomiting;
- 1351 • Less common (1-10%): dyspepsia, abdominal pain, abdominal distension, eructation,
 1352 flatulence; and
- 1353 • Rarely (<1%): gallbladder disease, acute pancreatitis

1354 All adverse effects are reversible with discontinuation of the medication.

1355 **Data and Safety Monitoring Committee (DSMC):**

- 1357 1. [name]
- 1358 2. [name]
- 1359 3. [name]
- 1360 4. [name]

1361 The DSMC will meet biannually by telephone/teleconference and distribute a report to the IRB
 1362 at the completion of each meeting.

1363 **LIABILITY AND SUBJECT INSURANCE:**

1364 During and following a subject's participation in the trial, the primary investigators (IN and SM)
 1365 and UT Southwestern Medical Center will provide adequate medical care to the study subject
 1366 for any study-related adverse events, including clinically significant laboratory values related to
 1367 the study. This medical care for study subjects will be provided regardless of their insurance
 1368 status.

1369
 1370 Novo Nordisk carries product liability insurance for its products. Sponsor-investigator agrees to
 1371 indemnify Novo Nordisk in accordance with the written contract executed between the parties
 1372 for this study. Generally, however, Novo Nordisk assumes no liability in the event of negligence
 1373 of the sponsor-investigator conducting the trial, or by persons for whom the sponsor-investigator
 1374 is responsible.

1375 **EVALUABILITY OF SUBJECTS:**

1376 The following analysis sets are defined:

1377 ***Full analysis set (FAS)***

1378 All randomized subjects exposed to at least one dose of the trial product and with at least one
 1379 post-baseline assessment of any efficacy endpoint will be included. Subjects in the FAS will be
 1380 analyzed according to intention to treat (primary) and per-protocol (secondary). The requirement
 1381 of a post-baseline observation is in alignment with the FDA recommendations.

1382 ***Safety analysis set***

1383 All randomized subjects who have been exposed to at least one dose of trial product. Subjects
 1384 in the safety analysis set will be analyzed "as treated".

1385 **PREMATURE TERMINATION OF TRIAL:**

1386 The trial will be prematurely terminated for the following reasons only:

- 1387 1. A serious threat to the safety of trial participants occurs that cannot be addressed in any

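### End-of-trial imaging of early leavers is requested in two sections but made conditional on 40 weeks of treatment in a third, and LOCF is not limited to serially measured endpoints

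*Protocol*

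**What the plan says.** **Imaging of early leavers.** Three sections of the protocol speak to it.

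- Subject Replacement: subjects who withdraw or become ineligible are asked to "return at the end of the trial period to complete the follow-up imaging/laboratory testing and" are then to be analysed by intention to treat.
- Visit Procedures: at premature withdrawal the Visit 16 procedures are to be done if possible. Those who stop before Visit 16 are also asked to attend a Visit 16x, 40 weeks after randomization, to record all outcome assessments where possible.
- Premature discontinuation: a visit at the time of stopping covers body weight, adverse events and a discussion of end-of-trial imaging. The imaging itself is offered on condition that the subject has had 40 weeks or more on trial treatment.

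**Analysis.** Under Statistical Methods, the "primary outcome will be analyzed using an intention to treat analysis". The full analysis set takes dosed, randomized subjects; those with at least one "post-baseline assessment of any efficacy endpoint will be included".

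**Schedule.** For Visit 3: "At this visit, they will undergo all baseline anthropometric, imaging, and laboratory assessments". Then "Visit 16 is the final visit during the maintenance phase during which follow-up imaging and" laboratory studies are done. The assessment table places VAT, the other MRI measures, insulin, CRP and NT-proBNP at these two visits only. Weight, blood pressure and heart rate are measured repeatedly from Visit 4.

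**Missing data.** The SAP is to describe "analytical approaches to address missingness of data, including multiple imputation including" "the last observation carried forward (LOCF) and mixed-effects model repeated measure" approaches. No endpoint is singled out.

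**The concern.** The imaging condition in Premature discontinuation cannot be met by the people that section is about. Visit 16, the end of treatment, falls at week 40 with a window of 3 days, so a subject who has had 40 weeks of treatment has in effect finished it. Read literally, the section offers a scan to almost nobody who stops early, while two other sections ask for that scan. Which text a site follows decides how many early leavers have a week-40 VAT value. An SAP cannot repair this afterwards, because a scan not taken at week 40 cannot be recovered.

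The missing-data list matters because it says what may be done about the scans that are absent. A subject who leaves after Visit 4 enters the full analysis set on the strength of a weight alone and may have no second scan. LOCF then has only the baseline scan to carry forward, which scores the subject as 0% change. If LOCF is restricted to post-baseline values, it imputes nothing. If a scan was taken at withdrawal, LOCF would let it stand in for week 40. Yet the sample size section expects VAT to fall by 8% even on placebo.

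**Working it through.** **Inputs** (Sample Size Calculation): VAT reduction of 8% on placebo and 16% on liraglutide, SD 16, two-sided 5%, 80% power, 1:1. The plan assumes that 28% "of subjects may withdraw trial medication during the trial, we expect a planned total of 178" are randomized.

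**The plan's own figures.** A two-sample t-test with standardized difference 8/16 = 0.5 needs 63.8, so 64 per arm and 128 in total. Then 128/(1 − 0.28) = 177.8, so 178. Both reproduce.

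**Scans at stake.** 178 × 0.28 = 49.8, about 50 subjects. If every one of them is scanned at Visit 16x, there are 178 week-40 scans. If none is, there are about 128. The 28% is a rate of medication withdrawal and drop-out, not of missing MRI, so 50 is an upper bound on what the contradiction can cost.

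**Effect of losing those scans.** Let a share d of each arm be unscanned and analyse observed scans only. If completers behave as planned, the observed difference is 8. The difference over all randomized subjects depends on where the unscanned subjects are at week 40. Placebo drop-outs are taken at −8% throughout.

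- Liraglutide drop-outs at −16%: 16 − 8 = 8.
- Liraglutide drop-outs at −8%: 16(1 − d) + 8d − 8 = 8(1 − d).
- Liraglutide drop-outs at 0%: 16(1 − d) − 8.

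**Effect of LOCF on VAT, if it were used.** With each unscanned subject set to 0%, the difference is 16(1 − dL) − 8(1 − dP), where dL and dP are the shares missing on liraglutide and placebo. With equal shares this is 8(1 − d).

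| | d = 10% | d = 20% | d = 28% |
|---|---|---|---|
| Observed scans only | 8 | 8 | 8 |
| LOCF | 7.2 | 6.4 | 5.76 |
| True difference, liraglutide drop-outs at −16% | 8 | 8 | 8 |
| True difference, at −8% | 7.2 | 6.4 | 5.76 |
| True difference, at 0% | 6.4 | 4.8 | 3.52 |
| LOCF minus truth, at −16% | −0.8 | −1.6 | −2.24 |
| LOCF minus truth, at −8% | 0 | 0 | 0 |
| LOCF minus truth, at 0% | +0.8 | +1.6 | +2.24 |

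Observed scans alone overstate the difference by 0.8, 1.6 or 2.24 points in the −8% case and by 1.6, 3.2 or 4.48 points in the 0% case. They are right in the −16% case. Only the missing scans could show which case applies.

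**Power under LOCF.** The arm variance is (1 − d)·256 + d(1 − d)·m², with m the planned reduction (16 or 8). With 89 per arm, the standard errors of the difference are 2.345, 2.275 and 2.206, and power by normal approximation is about 87%, 80% and 74%.

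**Unequal missingness.** Each extra percentage point missing on liraglutide lowers the LOCF difference by 0.16, and each on placebo raises it by 0.08. At an assumed 36% on liraglutide and 20% on placebo it is 16 × 0.64 − 8 × 0.80 = 3.84. With the shares reversed it is 16 × 0.80 − 8 × 0.64 = 7.68.

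**The case against.** **On imaging.** The condition could be a slip for 40 weeks since randomization, or could concern only what is offered at the discontinuation visit, with Visit 16x following regardless. Either is plausible, but neither is written, and the section never mentions Visit 16x. A reader might also infer that the trial becomes underpowered. The documents do not support that, because the sample size already allows for 28% loss and still keeps 128 completers. What is at risk is the intention-to-treat comparison.

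**On LOCF.** The protocol defers methods to an SAP that is not shown. It assigns no method to VAT, makes LOCF primary nowhere, lists multiple imputation and promises sensitivity analyses. The doubled wording is most naturally a loosely drafted list of three methods, and LOCF can be carried out for weight, blood pressure and heart rate. All of this stands, so the LOCF point is conditional. Three stronger readings go too far.

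- That the plan will score unscanned subjects as unchanged: no text says so.
- That LOCF would distort the result in a known direction: the table shows negative, zero and positive error, depending on where drop-outs end up.
- That LOCF also gives a misleading standard error as a separate fault. Simulated 95% intervals cover at 95% where the bias is zero. At 28% missing and a true difference of 8, bias alone (−2.24/2.206 = −1.015 standard errors) predicts coverage of about 82.6%, against 82.5% simulated.

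A mixed model for VAT alone is not wrong either. With one follow-up it adds nothing beyond a baseline-adjusted analysis of the observed scans.

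**Conclusion.** The contradiction over imaging is firm and rests on the text alone. Two sections seek an end-of-trial scan from early leavers, and a third offers it on a condition they cannot meet. Following the third could cost up to about 50 of 178 week-40 scans, assuming that the full 28% stop early and that none is otherwise scanned.

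The LOCF point is secondary and conditional. The list names a method that does not suit endpoints with one follow-up and does not confine it to the others. If it were applied to VAT with equal missingness, the planned 8 points would become 7.2, 6.4 or 5.76 at 10%, 20% or 28% missing, with 28% as the upper case. That assumes the planned means hold among those scanned and that every missing scan is set to no change. Whether the shrinkage is bias depends on the estimand. This is worth correcting, but it is not evidence of a wrong primary analysis.

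**What to change.** 1. Reconcile Premature discontinuation with Subject Replacement and Visit Procedures, so that the week-40 outcome assessment of subjects who stop early is stated once and consistently. This should be settled while such subjects can still be scanned.
2. Reword Missing Data so that multiple imputation, MMRM and LOCF appear as separate methods, and state that LOCF will not be used for endpoints with a single follow-up measurement.
3. For those endpoints, use retrieved week-40 values first. For what is still missing, use multiple imputation (already listed), informed by the baseline value and the serial body weights.
4. Leave the imputation model, any covariance adjustment, reference-based sensitivity analyses and the methods for serially measured endpoints to the SAP.

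The cost is protocol wording, a note to site staff and some programming. No new visit or measurement is needed: Visit 16x is already planned and the weights are already collected. The scans obtained at Visit 16x are a running cost that the plan has in principle accepted.

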765 The end of the clinical trial is defined as the last visit of the last subject (LPLV).
766

767 **Trial Sites:**

768 The trial will be conducted at three sites in Dallas, TX:

[figure not shown]
- 769 1. University Hospital Ambulatory Clinics (at Aston and St. Paul Professional Office
770 Buildings)
- 771 2. Clements University Hospital
- 772 3. Parkland Hospital and Ambulatory Clinics

774 **Visit Procedures:**

775 Prior to the first trial visit, potential subjects will be identified by physician referral or media
776 advertisement and will be introduced to participation in the trial by one of the trial staff. If the
777 patient meets potential inclusion criteria, written informed consent will be obtained and the
778 subject will be scheduled for Visit 1.
779

780 Subjects enrolled in the trial will be provided with a subject ID card, stating that they are
781 participating in a trial and whom to contact (site address, Investigator's name and telephone
782 number) for further information, if necessary. The subjects will be reminded to show the card to
783 other health care providers, as applicable. The subjects will be instructed to return the card to
784 the Investigator at the last visit of the subject or destroy the card after the last visit

785
786 The Investigator will keep a subject screening log and a subject enrolment log. For screening
787 failures (subjects who have given informed consent but who do not meet the inclusion,
788 exclusion and/or randomization criteria and hence are not randomized), all data for completed
789 trial procedures will be recorded in the case record form (CRF), and the reason for exclusion
790 from the trial will be recorded on the screening failure form. The screening failure form will be
791 entered into the clinical database.
792

793
794
795
796

Table: Visit Schedule

Visit no.	Time of Visit	Visit Type
1	-4 weeks \pm 5 days	Screening
2	-2 weeks \pm 3 days	Run-In
3	Day 0, baseline	Randomization
4	1 week \pm 3 days	Dose escalation
5	2 weeks \pm 3 days	Dose escalation

6	3 weeks ± 3 days	Dose escalation
7	4 weeks ± 3 days	Dose escalation/maintenance
8	8 weeks ± 3 days	Maintenance
9	12 weeks ± 3 days	Maintenance
10	16 weeks ± 3 days	Maintenance
11	20 weeks ± 3 days	Maintenance
12	24 weeks ± 3 days	Maintenance
13	28 weeks ± 3 days	Maintenance
14	32 weeks ± 3 days	Maintenance
15	36 weeks ± 3 days	Maintenance
16	40 weeks ± 3 days	End of treatment
17	42 weeks ± 3 days	Observational Follow-up/End of trial

797

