798 The total duration of the trial (for a subject completing the trial) will be up to 46 weeks and will
 799 comprise a total of 17 visits.

800

801 **Table: Treatment of subjects**

802

Trial periods	Screening	Run-In	Randomization	Dose escalation period/ Maintenance			Maintenance / End of treatment	Follow-up
Weeks in relation to Visit 2 (randomization)	-4	-2	0	1 2 3			4-40	42
Visit number	1	2	3	4 5 6		7-16	17	
Liraglutide	Screening	Run-In	0.6 mg	1.2 mg	1.8 mg	2.4 mg	3.0 mg	No treatment
Placebo			Placebo	Placebo	Placebo	Placebo	Placebo	

803

804 **Table: Visit schedule with assessments**

805

Prior to Screening Visit	Screening	Run-In	Randomization	Dose Escalation							Maintenance Period								End of Treatment	Observational Follow-up
				1	2	3	4	5	6	7	8	9	10	11	12	13	14	15	16	
Informed consent	X	X (review)																		
In/exclus	X																			

ion criteria																			
Randomi zation criteria				X															
Withdra wal criteria		X	X	X	X	X	X	X	X	X	X	X	X	X	X	X	X	X	
Demogr aphics																			
Age	X		X																
Sex	X		X																
Race	X		X																
Concomi tant illnesses/ Medical history		X		X	X	X	X	X	X	X	X	X	X	X	X	X	X	X	
Concomi tant medicati ons		X		X	X	X	X	X	X	X	X	X	X	X	X	X	X	X	
Measure ments																			
Height	X		X															X	
Weight	X		X	X	X	X	X	X	X	X	X	X	X	X	X	X	X	X	
Blood pressure	X		X	X	X	X	X	X	X	X	X	X	X	X	X	X	X	X	
Heart rate	X		X	X	X	X	X	X	X	X	X	X	X	X	X	X	X	X	
Blood glucose	X		X															X	
Triglyceri des	X		X															X	
HDL- cholester ol	X		X															X	
Pregnan cy test (if female)	X		X															X	
Waist circumfer ence				X														X	
Hip circumfer ence					X													X	
Visceral AT (MRI)					X													X	
Abd subcutan eous AT (MRI)					X													X	
Total fat				X														X	

mass (MRI)																
Total fat-free mass (MRI)				X												X
Lower body AT (MRI)				X												X
Hepatic fat (MRI)				X												X
Laboratory tests																
Fasting insulin				X												X
CRP				X												X
NT-proBNP				X												X
Trial Related																
Diet and physical activity counseling		X	X	X	X	X	X	X	X	X	X	X	X	X	X	X
Drug accountability				X	X	X	X	X	X	X	X	X	X	X	X	
Adverse events		X	X	X	X	X	X	X	X	X	X	X	X	X	X	X

806

807 At Visits 1, 3, and 16 the subject must attend the clinic in a fasting condition in the morning (i.e.,
 808 at least eight hours overnight fast without food and/or drink intake, except for water).

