809 Background medication should be withheld on the day of the fasting Visits 1, 3, and 16 until
 810 blood sampling has been done. At all other visits the background medication and trial product
 811 should be taken as usual during the conduct of the trial.

812

813 Trial product will be dispensed at visits 3 through 15. Subjects will be asked to bring all empty,
 814 partly used and unused trial product at visits 4 through 16 for drug accountability. The
 815 computerized randomization system should be contacted for trial product dispensing. If the
 816 subject attends the clinic for a visit not described in the protocol, then an Unscheduled Visit
 817 Form must be completed. The Unscheduled Visit Form should not be completed if the sole
 818 purpose of the visit is trial product dispensing. If an unscheduled visit is made for the purpose of
 819 dispensing trial products to the subjects then an unscheduled dispensing session must be
 820 completed in the computerized randomization system. If it is not possible to attend the visit
 821 within the visit window, the subjects should be called in for an Unscheduled Visit.

822

823 In case a subject is being prematurely withdrawn from the trial before or at visit 16, the
 824 Investigator will ensure that the procedures for the End of Treatment visit (Visit 16) are

825 undertaken, if possible. The primary reason (adverse event, non-compliance with protocol or
826 other) for discontinuation will be specified in the CRF and a computerized randomization system
827 withdrawal session should be completed. Even if the subject is not able to attend a final visit, the
828 End of Trial Form (EOT) must be completed.

829
830 Subjects that have discontinued the trial prematurely before Visit 16 will be asked to attend a
831 visit (Visit 16x) taking place 40 weeks after the randomization date. The purpose of this visit will
832 be recording of all outcome assessments if possible. If the subject is not willing to attend Visit
833 16x, it should be documented in the patient medical record that the subject has refused to
834 attend the visit.

835
836 **Visit 1**
837 At Visit 1, the informed consent will be reviewed again for signature and participants will be
838 screened for eligibility in the trial. This will include interview assessment for inclusion and any
839 exclusion criteria and laboratory components of the metabolic syndrome. Subjects that meet all

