- 970 • Abdominal subcutaneous adipose tissue mass
- 971 • Total fat mass
- 972 • Total fat-free mass
- 973 • Lower body adipose tissue mass
- 974 • Hepatic fat content
- 975 • Laboratory tests, including
 - 976 - Markers of insulin resistance: fasting blood glucose, insulin
 - 977 - Markers of inflammation: CRP
 - 978 - Lipids: TG/HDL-C ratio,
 - 979 - Natriuretic peptides: NT-proBNP

Visit 17

980 Visit 17 will be an observational follow-up visit during which subjects will be monitored for AEs.
 981 At the End of Trial visit (Visit 17) the Investigator or delegate will provide counseling on the
 982 management of weight control and follow-up medical care.

Assessments for efficacy

983 Weight will be recorded to the nearest 0.1 kg using calibrated scales. Weight will be measured
 984 in a fasting state with an empty bladder, without shoes and only wearing light clothing. Height
 985 without shoes will be recorded at Visit 1. BMI will be calculated as follows: BMI = weight
 986 (kg)/height (m²)

987 Systolic and diastolic blood pressure will be measured at all visits

- 988 • The auscultatory method should be used to measure blood pressure.
- 989 • The patient should avoid caffeine, smoking, physical activity for 30 minutes prior to
 990 measurement.
- 991 • Remove all clothing over the covered arm.
- 992 • The same sphygmomanometer should be used throughout the trial.
- 993 • The measurement should be taken in the seated position with legs uncrossed, back
 994 and arm supported.
- 995 • Subject should rest in a sitting position for 5 minutes prior to the first blood pressure
 996 being taken.
- 997 • The measurement should be in the upper arm with a stethoscope at the elbow
 998 crease over the brachial artery.
- 999 • The same arm should be used for blood pressure measurements at all trial visits.
- 1000 • The size of the cuff should be appropriate. The bladder of the cuff should encircle at
 1001 least 80% of the arm circumference and the width of the cuff is at least 40% of the
 1002 arm circumference.
- 1003 • The cuff placement must be preceded with palpation of the brachial artery and the
 1004 antecubital fossa. The midline of the cuff bladder must be placed over the location of
 1005 the arterial pulsation. The lower edge of the cuff should be 2 to 3 cm above the
 1006 antecubital fossa to allow for stethoscope placement.
- 1007 • The cuff placement must be preceded with palpation of the brachial artery and the

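### Weights are to be taken fasting, but fasting attendance is asked for only at Visits 1, 3 and 16, so the week-16 weight behind the 4% responder split may be non-fasting against a fasting baseline

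*Protocol*

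**What the plan says.** - **Weighing condition (Protocol, Assessments for efficacy).** Weight is recorded to 0.1 kg and measured "in a fasting state with an empty bladder, without shoes and only wearing light clothing. Height". The final word belongs to the following sentence, on height. No visit is singled out or exempted.
- **Fasting visits (text after the table headed "Visit schedule with assessments").** "At Visits 1, 3, and 16 the subject must attend the clinic in a fasting condition in the morning (i.e"; the parenthesis goes on to define an overnight fast of at least eight hours, water excepted. The same three visits are named again: "Background medication should be withheld on the day of the fasting Visits 1, 3, and 16 until" blood has been drawn. The next sentence covers the remaining visits, but only for background medication and trial product. It does not mention food.
- **Visit schedule.** Visit 3 is "Day 0, baseline". Visit 10 is "16 weeks ± 3 days", a maintenance visit. The weight row of the assessment table is marked across the visits from randomization on, although the table layout is broken in the text at hand.
- **Responder analysis (Statistical Methods).** Outcomes are to be stratified by whether the subject lost at least 4% of body weight: "weight at 16 weeks of treatment will be performed prior to unblinding to determine differential" outcomes between responders and non-responders.
- **Visit 16x (Visit Procedures).** Subjects who discontinue before Visit 16 are asked back 40 weeks after randomization so that all outcome assessments can be recorded. This visit is not on the fasting list either.

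**The concern.** The weighing rule presupposes that a subject arrives fasted whenever weight is taken. The attendance rule arranges for that at only three visits. Staff who work from the visit schedule have no reason to tell a subject to fast before Visit 10.

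For most visits this matters little. It matters at Visit 10 because that weight is compared with the Visit 3 weight and then cut at 4%. A hard cut-off is sensitive to small systematic differences between the two measurements. Food and fluid add weight, so a non-fasting follow-up weight set against a fasting baseline understates loss. The systematic part of the error runs one way, from responder to non-responder.

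The SAP cannot repair this afterwards. It is an instruction to sites and subjects, the visit lists of items to be recorded in the CRF contain no item for fasting state at weighing, and a weight already taken cannot be converted.

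**Working it through.** **Plan's own figure.** There is none to reproduce. The protocol gives no expected responder share, no mean or SD of week-16 weight loss, and no baseline weight.

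**Step 1: the weights that are compared.**

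| Use of weight | Visits compared | On the fasting list? |
|---|---|---|
| Secondary endpoints, change in body weight at 40 weeks | 3 and 16 | both |
| Same, early discontinuers who return | 3 and 16x | 3 only |
| 4% responder split | 3 and 10 | 3 only |
| Primary endpoint (VAT by MRI) | no weight used | not applicable |

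**Step 2: effect of a non-fasting weight at Visit 10.** Let W0 be the fasting baseline weight, W16 the fasting weight at week 16, and x the excess in kg if the subject is not fasted.

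Observed loss (%) = 100 × (W0 − W16 − x) / W0 = true loss − 100·x / W0

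The effective cut-off on true loss is therefore 4 + 100·x / W0. With *assumed* values of x and W0:

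| x (kg) | W0 = 80 kg | W0 = 100 kg | W0 = 120 kg |
|---|---|---|---|
| 0.3 | 4.38% | 4.30% | 4.25% |
| 0.5 | 4.62% | 4.50% | 4.42% |
| 1.0 | 5.25% | 5.00% | 4.83% |
| 1.5 | 5.88% | 5.50% | 5.25% |

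If the weight is taken fasting, x = 0 and the cut-off stays at 4%.

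**Step 3: share that would change group.** Take true loss as normal with mean m and SD s, and a common offset d = 100·x / W0. The share moving from responder to non-responder is P(4 ≤ loss < 4 + d) = Φ((4 + d − m)/s) − Φ((4 − m)/s). All inputs are *assumed*.

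Share classed as responder, s = 4:

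| m | d = 0 | d = 0.5 | d = 1.0 | d = 1.5 |
|---|---|---|---|---|
| 6% | 69.1% | 64.6% | 59.9% | 55.0% |
| 3% | 40.1% | 35.4% | 30.9% | 26.6% |

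For example, with m = 6 and d = 1.0: Φ((6 − 5)/4) = Φ(0.25) = 59.9%, against Φ(0.5) = 69.1% with no offset.

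Over a wider grid (m of 2, 4 and 6%; s of 3, 4 and 5%; d from 0.3 to 1.5 points), the share of all subjects changing group runs from 2.2% (for instance m = 6, s = 5, d = 0.3) to 19.1% (m = 4, s = 3, d = 1.5). At m = 4, s of 4 to 5 and d of 0.5 to 1.0, it is 4.0% to 9.9%.

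These figures assume that every subject is non-fasting at Visit 10 by the same amount. If only some are, the shift is smaller. They describe the grouping only, not the treatment comparison within groups.

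**The case against.** A reader might infer that the week-16 weight *is* non-fasting and that responders *are* misclassified. The documents do not support that. No text says the Visit 10 weight will be taken after food. Read literally, the rule under Assessments for efficacy requires it to be fasting, and the split would then compare like with like.

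Nor is it right that the two rules cannot both be followed. The three listed visits are those with blood tests, and the text ties the withholding of medication to blood sampling. Nothing forbids fasting at other visits. A site can meet both rules by having subjects fast whenever weight is taken.

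The reach is also narrow. The primary endpoint uses no weight, and scheduled attenders' 40-week weight change rests on two listed fasting visits. What is exposed is one supplementary analysis, split on a post-randomization variable, in which both blinded arms follow the same schedule. Interim weights could also enter a carried-forward or repeated-measures analysis of body weight, but the protocol leaves those methods to the SAP. The percentages above rest wholly on assumed inputs.

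All of this stands, and it limits the point to a conditional one. It does not remove it: the general rule asks for fasting weights, the specific schedule does not arrange for them, and a site that follows the schedule can depart from the rule without noticing.

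**Conclusion.** The point holds as an inconsistency to be reconciled, with a conditional consequence. The protocol requires fasting weights in general but asks for fasting attendance only at Visits 1, 3 and 16. The Visit 10 weight that sets the 4% groups may therefore be non-fasting against a fasting Visit 3 baseline. If so, loss is understated and borderline responders could be counted as non-responders.

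The documents do not allow the size to be derived. The 2% to 19% range depends on an assumed weight-loss distribution and an assumed uniform offset, and it is zero if sites weigh subjects fasted at Visit 10. Neither the MRI primary endpoint nor the Visit 3 to Visit 16 weight change of subjects attending as scheduled is affected. This is a minor point, worth making because it is cheap to settle before data are collected and cannot be corrected afterwards.

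**What to change.** Reconcile the two sections by adding Visit 10 and Visit 16x to the visits at which subjects attend fasting. The 4% classification would then compare fasting with fasting weight, and so would the week-40 weight change of early discontinuers who return. The sentence on withholding background medication names the same visits and is tied to blood sampling. The amendment should state explicitly whether it extends to the added visits, so that it does not change by accident.

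**Cost.** One additional overnight fast per subject, at Visit 10, and a line or two of text. Visit 16x adds little, since the outcomes to be recorded there include fasting blood glucose.

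**Not recommended.** The conflict should not be resolved by declaring that only the weights from Visits 3, 10 and 16 count for efficacy. With 28% drop-out expected, that would discard interim weights that a carried-forward or mixed-model analysis could use. It could also remove subjects who leave before week 16 from the full analysis set, which requires at least one efficacy assessment after baseline.
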